3.5.2 Dose Interruption

Unscheduled dose interruptions are permitted on this clinical trial as deemed necessary by the investigator. If a dose interruption occurs this should be recorded and reason for the interruption documented. Dose interruptions are permitted up to 14 days to correct mechanical issues with the pump or catheter, as well as pump replacements if necessary. Supportive oral, intravenous or transdermal medication may be given to manage pain and withdrawal symptoms at the discretion of the investigator.

3.5.3 Pump or Catheter Replacements

Pump or catheter replacements are permitted in this trial due to mechanical malfunctions, battery failures or other related mechanical reasons. The Medical Monitor should be notified if any subject requires a surgical procedure to correct a catheter failure or requires a pump replacement.

Protocol CNS-HYD202US

Version: 7.0

If a subject requires a pump replacement or catheter replacement, drug interruptions for up to 14 days are permitted while the procedure is conducted and study drug can be replaced into the new pump. If the pump is removed, drug within the pump should be discarded and replaced with investigational product from a new vial(s) of hydromorphone hydrochloride. Investigational drug wasted from the pump should be documented for accurate drug accountability. After the pump or catheter replacement, at the discretion of the investigator, subjects may be restarted at their previous dose of hydromorphone hydrochloride or a reduced dose and titrated back to a therapeutic dose as part of normal standard of care for that subject after the pump or catheter replacement.

3.6 Concomitant Medications

3.6.1 Prior and Concomitant Medications

Prior medications are defined as medications that were taken within 30 days prior to initial dosing with study drug.

Concomitant medications are defined as medications taken any time after the start of dosing until the final visit.

While there is minimal published systematic experience with the use of intrathecal hydromorphone hydrochloride in combination with other medications the practice of giving combinations of products in intrathecal pumps to manage pain symptoms is common. Physiological interactions attributed to the combined use of intrathecal hydromorphone hydrochloride and other epidural analgesics may include excessive sedation, hypotension and respiratory depression.

3.6.2 Concomitant Medications Permitted to be Combined with Hydromorphone Hydrochloride in the Pump

If additional therapeutic agents are needed to achieve optimal analgesic effect, it is permissible to use a concomitant medication added to the hydromorphone hydrochloride to be used through the intrathecal route. Naïve subjects will need to be titrated to a therapeutic dose that is well tolerated prior to starting intrathecal combination therapy. All other subjects on combination therapies may maintain their combination therapy regimen upon conversion to study medication. A list of drugs commonly combined with hydromorphone hydrochloride and administered through intrathecal pumps is provided below:

morphone Hydrochloride Version: 7.0

Protocol CNS-HYD202US

- Bupivacaine
- Fentanyl
- Clonidine
- Baclofen
- Gabapentin
- Ropivacaine

Other concomitant medications should be avoided during the conduct of this study.

3.6.3 Prohibited Concomitant Medications

During treatment with intrathecal hydromorphone hydrochloride, subjects should avoid sedatives, hypnotics, phenothiazines, anesthetics, tranquilizers or other drugs that may induce hypotension or depressive effects. Subjects should be advised to avoid excessive alcohol consumption while on therapy.

Agonist/antagonist analgesics (i.e. pentazocine, nalbuphine, butorphanol, and buprenorphine) should be administered with caution to a subject who has received or is receiving a course of therapy with a pure opioid agonist analgesic such as hydromorphone hydrochloride. In this situation, mixed agonist/antagonist analgesics may reduce the analgesic effect of hydromorphone hydrochloride and/or may precipitate withdrawal symptoms in these subjects.

Opioids can interact with drugs that increase the effects of serotonin (see Section 1.3.1). These include antidepressants such as selective serotonin reuptake inhibitors (SSRIs), serotonin and norepinephrine reuptake inhibitors (SNRIs), tricyclic antidepressants (TCAs), monoamine oxidase (MAO) inhibitors, mirtazapine, and trazodone; triptans (migraine medication); 5-HT3 receptor antagonists (antiemetic drug); tramadol (analgesic drugs); linezolid (antibiotics); and intravenous methylene blue (antidote for methemoglobinemia). The interaction could cause a rare but potentially life-threatening condition called serotonin syndrome. All such medications should be administered with caution⁵³.

3.7 **Duration of Therapy**

In the absence of a granuloma or intolerable related AEs (Adverse Drug Reactions) subjects in this trial may continue on treatment for approximately 365 days after Day 1 of this trial.

3.8 Procedures for Monitoring Subject Compliance

Subjects will return to the clinic for scheduled visits and pump refills as specified in Appendix A, but pumps may be filled sooner if necessary or for scheduling purposes. Subjects who do not comply with the visit schedule will be discontinued from the study, weaned off study medication, and can receive another treatment at the discretion of the attending physician caring for the patient.

01 August 2016 34 CONFIDENTIAL

4.0 STUDY POPULATION

Male or female subjects requiring intrathecal opioid treatment to manage chronic moderate-to-severe intractable pain, 18 to 75 years of age.

Protocol CNS-HYD202US

Version: 7.0

4.1 Inclusion Criteria

For a subject to be eligible for this study, s/he must meet all of the following criteria:

- 1. Subjects must be at least 18 years of age and no more than 75 years old.
- 2. Clinically diagnosed with moderate-to-severe intractable pain for at least a 6-month period.
- 3. Subject is reasonably expected to benefit from intrathecal pain medication and has a SynchroMed II programmable intrathecal pump.
- 4. Subject agrees to sign a Pain Treatment Agreement (Narcotic Contract) limiting narcotic prescriptions to the study medication prescribed by the investigator.
- 5. Subject must be cognitively intact and, in the opinion of the investigator, capable of participation in the trial.
- 6. Female subjects of child-bearing potential must agree to use a medically acceptable and effective double-barrier method of birth control.
- 7. Subjects who can receive an MRI (with and without contrast) or CT myelogram.
- 8. Provides written Ethics Committee approved informed consent.
- 9. Willing to comply with all study procedures and requirements.

4.2 Exclusion Criteria

Subjects who meet any of the following criteria will be excluded from participation in the study:

- 1. Women who are pregnant or breast-feeding.
- 2. Subject has any known or suspected allergy to hydromorphone hydrochloride or to the materials of the infusion pump or intrathecal catheter.
- 3. Subject has a history of dependence and abuse of opioids, stimulants, alcohol, or benzodiazepines, as defined by DSM-IV criteria, within the past year (physical dependence on prescribed opioid analgesics is allowed but abuse of opioids according to DSM-IV is not permitted, ie, opioid addiction for recreational use).
- 4. Subjects who show signs of active systemic infection.
- 5. Subjects with a metastatic cancer to the spinal canal or a known central nervous system contraindication to intrathecal therapy.
- 6. Subjects have a condition requiring diathermy procedures.
- 7. Subject has a life expectancy of less than 12 months.
- 8. Subjects who are unable or unwilling to return to all of the required follow-up visits.
- 9. As a result of medical review and physical examination, the Investigator considers the subject unfit for the study.

01 August 2016 35 CONFIDENTIAL

5.0 SAFETY ASSESSMENTS

5.1 Collection of Adverse Events Data

Data regarding treatment-emergent AEs will be collected in this study. Treatment-emergent AEs are events that are not present at baseline, or if present at baseline, have worsened in severity. AEs will be assessed at each study visit from the time of study drug administration, during optional titration days, and for the long-term safety period starting on Study Day 1 through the final visit. AEs assessed by the Investigator as related to study drug and "ongoing" at the final scheduled study visit will be monitored by the Investigator until resolved or stabilized.

Protocol CNS-HYD202US

Version: 7.0

Each subject will be observed and queried by the Investigator or his/her designee at each study visit for any continuing AEs or new AEs since the previous visit. If an AE occurs between study visits, regardless of causal relationship to study drug and in the opinion of the Investigator, requires a study visit for full evaluation, the subject will be asked to return to the site for an unscheduled visit.

Any AE reported by the subject or noted by the Investigator or his/her designee will be recorded. The following information will be recorded for each AE: description of the event, date and time of onset, date and time of resolution, severity, causal relationship to study drug, outcome, action taken with the study drug and any treatment given.

All abnormal changes from baseline in physical examination findings including vital signs will be collected, graded with regards to severity or clinical significance, assessed for causal relationship, and will be recorded.

5.2 Physical Examinations and Medical History

5.2.1 Complete Physical Examination

The Investigator or designee will perform a complete physical examination at screening. Results will be recorded as part of the Medical History. Assessments of height, weight, calculation of body surface area (BSA), and vital signs will be recorded. Any underlying medical condition will be recorded as ongoing baseline events for future assessment of adverse events or serious adverse events. Only adverse changes from this baseline condition will be considered adverse events or serious adverse events.

5.2.2 Medical History

A medical history will be obtained at screening. For subjects entering the CNS-HYD202US trial from the CNS-HYD201US trial, medical history will be imported from the previous trial and does not have to be repeated.

Medical history will include demographic data (age, gender, race/ethnicity, etc.). In addition to general medical conditions, specific information relative to the underlying disease that resulted

in severe intractable pain requiring an intrathecal pump will be obtained and recorded in the CRF:

- Underlying disease, injury or condition resulting in intractable pain, date of initial diagnosis, and prior treatments.
- Date of implantation of an intrathecal SynchroMed II pump. If a previous pump was removed and a new pump has been implanted, the date of each implantation and reason for removal is requested.
- Date of surgical interventions for treatment of intractable pain.
- History of prior opioid use (oral, transdermal or intravenous) prior to implantation of the pump.
- Other significant medical history.

5.3 Vital Signs and ECG

Systolic and diastolic blood pressure, radial pulse, breathing rate and temperature will be obtained at baseline and each study visit and recorded. All vital signs will be obtained in a semi-recumbent position.

An ECG will also be obtained at screening to assess any cardiovascular abnormalities for the purposes of determining eligibility for this trial.

5.4 Documentation of Prior Concomitant Medications

Details regarding the name, indication, dose, route of administration, and frequency of all prescription medications within the past 30-days will be recorded. For subjects entering the CNS-HYD202US trial from the CNS-HYD201US trial, medical history will be imported from the previous trial and does not have to be repeated.

6.0 PHARMACOKINETICS

No pharmacokinetic assessments will be conducted during this trial.

7.0 PHARMACODYNAMICS

Other than pain evaluation, no pharmacodynamic assessments are planned during this trial.

8.0 EFFICACY

There is no efficacy endpoint in this trial given the open-label nature of the study. Subjects will be given a VASPI at scheduled time periods and generally during visits to the clinical site.

9.0 STUDY VISITS

Refer to Appendix A for the Schedule of Study Procedures.

9.1 Screening

The Investigator or his/her approved designee must explain the nature of the study protocol and associated risks to the potential study participant. The potential participant must be allowed to review the study information and to ask questions before being asked to sign the Informed Consent Form. Written informed consent must be provided by the potential study participant or legal guardian prior to initiation of any screening evaluations or other study-related procedures that are not considered standard of care assessments. The signature, date, and the name of the individual(s) who obtained the informed consent will be recorded in the subject's medical record.

Protocol CNS-HYD202US

Version: 7.0

Screening, baseline, and initiation of dosing (Day 1 or optional titration day) may be combined as one visit for this trial. Laboratory testing is obtained as part of the baseline status of the subject for future adverse event evaluation, however, laboratory test results are not required for entry criteria and thus the subject may be enrolled prior to results being obtained.

For subject entering this trial from the CNS-HYD201US trial, informed consent may be obtained up to 30-days prior to the transition to this study. Screening, baseline and Day 1 assessments for this trial will be conducted as part of the final visit of the CNS-HYD201US study as indicated in Appendix A. Subjects transitioning from the CNS-HYD201US trial will retain their subject number from that study for the long-term safety trial.

For all other subjects not transitioning from CNS-HYD201US, after written informed consent is obtained, the subject will be assigned a subject number (SS-XXX) by the site and will undergo the designated screening procedures listed in Appendix A within 14 days prior to initiation of weaning or start of study drug administration. The Investigator will assess the results of these screening evaluations to determine eligibility for entry into the study according to the inclusion/exclusion criteria listed in Section 4.0. Screening procedures may be combined with baseline assessments and enrollment (Day 1 or optional titration day) in this trial.

9.2 Baseline Evaluations

If the subject is determined to be eligible for participation in the study they will undergo baseline assessments prior to study drug administration. Baseline assessments will be conducted according to the procedures outlines in Appendix A.

Note that the Screening, Baseline and/or the first day of dosing (enrollment) may be combined at one visit.

Note that for randomized subjects entering the CNS-HYD202US trial from the CNS-HYD201US trial, a physical examination and vital signs will be completed on the final visit day of the CNS-HYD201US trial, which is Day -1 of the CNS-HYD202US trial. However,

those subjects dropping out of CNS-HYD201US prior to randomization will need to do all assessments and meet all subject selection criteria in the current trial. Their assessments for CNSHYD201US will not carry over.

9.3 Dose Titration Period (Optional Titration Days)

Subjects requiring dose titration onto hydromorphone hydrochloride for injection will return to the investigational site every 3 to 14 days for dose adjustments. These dose adjustment days are considered Optional Titration days in the Schedule of Study Procedures (Appendix A).

Subjects who are not participating in the CNS-HYD201US trial, and are naïve to intrathecal medications or have been weaned off current intrathecal medications, will have the pumps filled initially with a 2 mg/mL hydromorphone hydrochloride for intrathecal injection. Subjects requiring titration from a low dose will be initiated on a dose between 0.1 mg/day and 0.5 mg/day, based on their current oral opioid dose and at the discretion of the investigator. These subjects will be allowed up to five (5) Optional Titration periods to achieve a therapeutic dose of hydromorphone prior to starting the long term safety period on Day 1 of this study. Dose adjustments thereafter will be allowed at regular scheduled visits by adjusting the pump speed with a maximum dose adjustment of 50% for doses up to 0.5 mg/day and 25% for doses above 0.5 mg/day.

For subjects who are entering this study from the CNS-HYD201US trial or who are converting directly from compounded hydromorphone hydrochloride (eg, Dilaudid[®]), the starting dose will be based on their prior dose. For subjects who have been weaned off therapy or are at a dose below what is considered adequate to treat their chronic pain, or are on other Intrathecal opioids, will need to be switched to hydromorphone hydrochloride Intrathecal Injection first and may require one or more Optional Titration days (See Schedule of Study Events in Appendix A). Once a dose that achieves adequate pain relief is determined, the subject will start at Day 1 of this study and continue per the Schedule of Study Events. Dose adjustments thereafter will be allowed at regular scheduled visits by adjusting the pump speed with a maximum dose adjustment of 50% for doses up to 0.5 mg/day and 25% for doses above 0.5 mg/day.

Prior to a dose adjustment above 1 mg/day, the pump should be drained and refilled with 10 mg/mL hydromorphone hydrochloride undiluted and pump speed adjusted to achieve the target dose. Dose adjustments may continue as needed to optimize the therapy. It is recommended that naïve subjects that are titrated onto hydromorphone hydrochloride be maintained on a monotherapy until on a therapeutic dose of hydromorphone hydrochloride. After titration and stabilization, other drugs may be included in the intrathecal pump (see Section 3.6.2) as part of the therapy if judged necessary by the primary investigator.

Oral opioid medication may be prescribed as needed during the dose titration phase. Other FDA approved non-opioid oral pain medications are permitted during this period in accordance with their marketed product labeling.

9.4 Long-Term Follow Up Period (Day 1 to Day 365)

After the titration period (if required based on the investigators discretion) subjects will start Day 1 of this trial and remain on continuous intrathecal treatment for the next 365 days or until withdrawal from the trial. Subjects may have their dose of intrathecal hydromorphone hydrochloride adjusted upwards or downwards during this period as necessary to obtain optimal pain relief and manage side effect, provided the dose does not exceed 10 mg/day (eg, 1.0 mL/day of 10 mg/mL hydromorphone hydrochloride for injection). Oral opioid supplemental medication may be prescribed as necessary and appropriate according to the practice of medicine. As needed other intrathecal medications (see Section 3.6.2) may also be added as deemed appropriate by the investigator with the drug generic name and daily dose recorded. Other FDA approved nonopioid oral pain medications are permitted during this period in accordance with their marketed product labeling.

Protocol CNS-HYD202US

Version: 7.0

Study procedures and assessments during this period are conducted according to Appendix A. Pump refills during this period are conducted as needed to maintain the appropriate volume of product in the pump and maintain the subject dosing. Additional unscheduled visits for dose adjustments, titration or to assess potential complications are permitted as needed.

All visit dates during the long term follow-up period are to be conducted within 7 days of the scheduled date (ie, \pm 7 days).

9.5 Final Visit

Subjects will return to the investigational site for the final visit at approximately Day 365 (12 months after long term treatment starts) or when discontinued from the study for any reason. At the final study visit subjects will be assessed for AEs and clinical signs or symptoms of a granuloma as well as other procedures according to Appendix A. At the final study visit, the investigator will remove the residual study drug from the subject's pump and will replace the study drug with standard of care medication/therapy.

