Subjects will be screened and evaluated for study participation prior to administration of any study medications. After signing an informed consent, and confirming eligibility and conformance with all entry criteria, the subject will be enrolled in the trial. For trial subjects participating in the CNS-HYD201US trial only baseline assessments that are not already conducted as part of the CNS-HYD201US trial Day 119 or Study Termination assessments will be performed. However, those subjects dropping out of CNS-HYD201US prior to randomization will need to do all assessments and meet all subject selection criteria in the CNS-HYD202US trial. **Study Visit** Their assessments for CNSHYD201US will not carry over. Schedule Subjects entering the CNS-HYD202US study may either stay on their current hydromorphone (See Appendix A: hydrochloride therapy, be directly switched to hydromorphone hydrochloride from other opioid Schedule of therapies, or will be titrated onto hydromorphone hydrochloride therapy as needed. Naïve subjects Study will need to be titrated to a therapeutic dose that is well tolerated prior to starting intrathecal Procedures) combination therapy. All other subjects on combination therapies may maintain their combination therapy regimen upon conversion to study medication. Subjects will return to the clinic according to the schedule in Appendix A to have dose adjustments and study evaluations. For subjects converted to a hydromorphone hydrochloride equivalent dose based on a 1:12 ratio, who require titration prior to achieving a therapeutic dose of hydromorphone hydrochloride, up to five (5) optional titration days are allowed prior to starting Day 1 of the study. The subject may continue dose adjustments to optimize treatment during the 365 day continuous dosing period to evaluate long-term safety of intrathecal hydromorphone hydrochloride. It is planned that each subject will participate in the study for approximately 12 months with expanded access after this period permitted at the discretion of the subject and attending physician and **Study Duration** Mallinckrodt Pharmaceuticals. Overall duration of the study may be up to approximately 24 months not including the expanded access, depending on the rate of enrollment and number of subjects enrolled. Subjects will be assessed throughout the study for adverse events and potential clinical signs and symptoms of a granuloma. Safety will be assessed through collection of AEs and SAEs during the conduct of the trial. At each visit, the subject will be gueried for any AEs that differ from their baseline condition at the time of enrollment into the trial. The use of intrathecal morphine has been associated in rare cases with a granuloma at the catheter tip that can result in serious neurological impairment, including paralysis. In this study, the potential for a granuloma will be assessed at each visit to the investigator. If a granuloma is suspected based on clinical signs and symptoms, an MRI (with and without contrast) or CT myelogram should be obtained to evaluate if a granuloma is present. Clinical signs and symptoms that may indicate a granuloma include: A sudden decrease in therapeutic response requiring increased daily doses that is not attributed to other assignable causes (eg, mechanical failures, catheter movement or catheter Safety Assessments blockages). Unexplained pain at the dermatomal level of the catheter tip. Unexplained neurological deficit or dysfunction that could be due to compression of the spinal cord at the level of a catheter tip. For the purpose of this study, confirmed granuloma is an intramural extra-medullary mass at the catheter tip that is confirmed by an MRI (with and without contrast) or CT myelogram as read by central independent radiologist, or by surgery. If only clinical signs are detected, but the granuloma or mass cannot be verified by MRI (with and without contrast) or CT myelogram, and no other cause can be determined, the event will be classified as a suspected granuloma. During the trial, all SAEs reported to the investigator shall be reported to the Sponsor or their delegate within 24-hours of the

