10.0 PREMATURE DISCONTINUATION FROM STUDY

A subject may be involuntarily discontinued from the study for the following reasons, at the discretion of the investigator and the Sponsor:

- Noncompliance with study procedures and visits to the investigational site
- Significant safety event that does not resolve within 7 days of lowering the dose or other clinical interventions.
- Lost to follow-up after every attempt has been made to contact the subject including sending a registered letter.
- Subject withdraws consent.

The reason for the discontinuation should be recorded.

The Principal Investigator and the Institutional Review Board/Ethics Committee (IRB/EC) reserve the right to prematurely terminate the study in the interest of subject safety and welfare. The Sponsor reserves the right to prematurely terminate the study at any time for administrative reasons. If subjects are discontinued, they will be titrated off of hydromorphone hydrochloride therapy and placed on other alternative treatments at the discretion of the investigator and according to standard medical practice and manufacturer instructions for the intrathecal pump.

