13.0 SAFETY MONITORING AND ADVERSE EVENTS

13.1 Adverse Events

Data regarding treatment-emergent AEs will be collected in this study. Treatment-emergent AEs are events that are not present at baseline, or if present at baseline, have worsened in severity.

The descriptions and grading scales found in the Common Terminology Criteria for Adverse Events (CTCAE) v 4.03 will be used for AE reporting. A copy of the CTCAE v 4.03 is provided in Appendix B.

The medical monitor and contact information for this study are presented below:

[name], MD	Medical Director, Social & Scientific	Office: [contact] [contact]	E-mail: [contact]
	Systems, Inc. [name] 20910		

Definition of Adverse Events and Adverse Drug Reactions:

Adverse events in the CRF will be classified according to the most recent FDA definitions and in a manner consistent with ICH guidelines. As such the following definitions will be used:

An adverse event (AE) is any unfavorable and unintended sign, symptom, or disease temporally associated with the use of an investigational (medicinal) product (IP) or other protocol-imposed intervention, regardless of attribution. An AE may include intercurrent illnesses or injuries that represent an exacerbation (increase in frequency, severity, or specificity) of pre-existing conditions (worsening of asthma). A laboratory abnormality will be reported on the "Adverse Event" case report form only if it is associated with clinical sequelae or requires therapeutic intervention. Whenever possible, it is preferable to record a diagnosis as the AE term rather than a series of symptoms relating to a diagnosis. AEs will be graded according to the NCI Common Terminology Criteria for Adverse Events (CTCAE) v 4.03.

The reporting period for AEs starts after the first administration of study drug on Day 1 and ends after discontinuation of study medication.

SAEs must be followed until resolution by the PI, even if this extends beyond the study-reporting period. Resolution is defined as the return to baseline status or stabilization of the condition with the expectation that it will remain chronic.

The investigator will assess AEs for severity, for relationship to Investigational Product (IP), and as to whether the event meets one or more of the definitions of an SAE. The investigator will determine the relationship of an AE to the IP and will record it on the source documents and AE CRF, using the categories defined below.

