- c. Optional titration days are intended for subjects requiring titration after switching from other opioids or control arm subjects enrolling after completion of the CNS-HYD201US trial. Titration days are only if needed to achieve a therapeutic dose of hydromorphone after which subjects will start on Day 1 of the trial. Optional titration days may be scheduled from 3 to 14 days apart depending on the investigator discretion.
- d. Day 1 of the trial is considered the first day of the long term extension period. All subjects should be titrated to a therapeutic dose prior to starting Day 1. Day 1 may include a dose adjustment as needed.

- e. Informed consent for subjects entering the CNS-HYD202US trial after completion of the CNS-HYD201US trial may be obtained as early as 30 days prior to completion of the CNS-HYD201US trial
- f. For subjects entering the CNS-HYD202US trial from the CNS-HYD201US trial, medical history will be carried over from the previous trial and does not need to be repeated.
- g. For subjects entering the CNS-HYD202US trial from the CNS-HYD201US trial, Physical Examination, will be completed on the final visit day of the CNS-HYD201US trial, which is Day -1 of the CNS-HYD202US trial.
- h. Pump refills will be conducted as necessary to adjust the treatment regimen and conduct pump refills. Pump refills are not required at all visits.
- i. Dose adjustments are allowed during the long-term follow up period both as an increase or decrease to optimize the dose. The maximum dose is 10 mg/day of hydromorphone hydrochloride.
- j. If there are clinical signs of a granuloma as defined in Section 3.3, the Medical Monitor should be notified and an MRI (with and without contrast) or CT myelogram scheduled to confirm the pathology of the granuloma.
- k. VASPI, COWS, BPI and PGIC are administered at the study site on specified visits.
- 1. At the final study visit, the investigator will remove the residual study drug from the subjects pump and will replace the study drug with normal standard of care medication/therapy.

01 August 2016 CONFIDENTIAL

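### For subjects who stop early, the protocol gives conflicting end-of-treatment handling and no order for taper, drug removal and final assessment, and the SAP pools these records with Day 365 completers

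*Protocol*

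**What the plan says.** Protocol 9.5 brings subjects back "for the final visit at approximately Day 365 (12 months after long term treatment starts) or when discontinued from the study for any reason". At that visit they are assessed, and "the investigator will remove the residual study drug from the subject's pump and will replace the study drug with standard of care medication/therapy". Footnote l of the Schedule of Study Procedures (Protocol Appendix A, repeated under SAP Table 1) says the same: the investigator "will replace the study drug with normal standard of care medication/therapy".

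Protocol 10.0 reads differently: "If subjects are discontinued, they will be titrated off of hydromorphone hydrochloride therapy and placed on other alternative treatments", at the investigator's discretion and following standard practice and the pump manufacturer's instructions. Protocol 3.8 says that subjects who do not keep to the visit schedule "will be discontinued from the study, weaned off study medication". Protocol 11.0 requires final-visit procedures for anyone who stops study drug early, but does not place them relative to a taper.

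The synopsis (Study Duration) describes about 12 months of participation, "with expanded access after this period permitted at the discretion of the subject and attending physician" and the company. Section 9.5 and footnote l make no exception for such subjects.

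On the analysis side, SAP 9.6.1 to 9.6.3 summarize VASPI, BPI and PGIC by visit, including the final visit. SAP 9.7 summarizes COWS total score and its change from baseline to the final visit. None of these sections separates a Day 365 visit from an early-termination visit.

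**The concern.** A subject discontinued before Day 365 falls under both 9.5 (remove and replace at the visit) and 10.0 (titrate off). One site could assess such a subject at the working dose and then empty the pump. Another could taper first and assess at a reduced dose or off drug. Both would file the result as the final visit.

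What is at stake is the meaning of the final-visit rows. A COWS score taken before removal cannot show withdrawal caused by removal, and no later COWS is scheduled. A score taken during or after a taper can show it. Pain scores raise the same question: is the change from baseline a result of treatment, or of treatment being withdrawn?

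**Working it through.** The plan states no figure on this point, so the check is mainly a comparison of texts.

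**1. Which rule applies to whom**

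| Source | Who | What happens to study drug |
|---|---|---|
| Protocol 9.5; footnote l (also SAP Table 1) | Everyone with a final visit; 9.5 includes those discontinued | Removed and replaced at the visit |
| Protocol 10.0 | Discontinued subjects | Titrated off, then alternatives |
| Protocol 3.8 | Subjects not keeping to the visit schedule (a subset of 10.0) | Weaned off |
| Protocol 11.0 | Anyone stopping study drug early | Final-visit procedures; timing against a taper not stated |
| Synopsis | After the 12-month period | Expanded access permitted |

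The first four rows overlap for early discontinuers. The last does not bear on them.

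**2. Can 9.5 and 10.0 both be followed?** Once residual drug is removed at the visit, none is left in the pump to titrate. That leaves three readings:
- the taper comes before the visit, and assessments are made at a reduced dose or off drug;
- there is no taper of study drug, and assessments are made at the working dose;
- any titration after the visit uses another product, and assessments are again made on study drug.

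The protocol does not choose among them. The June 2015 site-closure letter in SAP Appendix B asks for final visits and for study drug to be removed and replaced in sponsor-discontinued subjects. It does not mention titration.

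**3. Completers.** Section 9.5 describes assessment in the sentence before removal. The taper wording in 10.0 and 3.8 covers discontinued subjects only. A Day 365 completer is plausibly assessed on drug whatever follows.

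**4. Which outcomes are exposed.** VASPI, BPI and PGIC also have earlier post-Day 1 visits, so only their final-visit rows are affected. COWS is scheduled at baseline, on titration days and at the final visit, so after titration the final visit is its only reading. The COWS table (14.3.5.8) is listed for the ITT population alone, so it includes subjects from closed Site 028.

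**5. Scale.** Inputs are from Protocol 14.1: about 350 enrolled, 300 completing 6 months.
- 350 − 300 = 50, and 50/350 = 14.3%. This is an enrolment margin worked back from the targets, not a stated dropout rate. It does not count departures between 6 and 12 months.

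**6. Illustration, on assumed values.** Let f be the share of final-visit records taken during or after a taper, and D the mean difference on VASPI between those records and on-drug records. The pooled final-visit mean then differs from the on-drug mean by f × D.

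| f | D = 5 mm | D = 10 mm | D = 20 mm |
|---|---|---|---|
| 14.3% | 0.7 | 1.4 | 2.9 |
| 30% | 1.5 | 3.0 | 6.0 |

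Neither f nor D is in the documents. The table shows only how the two combine.

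**The case against.** The strongest reply is that 9.5 and 10.0 can be read together. Section 10.0 leaves the taper to the investigator's discretion and standard practice, while 9.5 says what happens to drug left in the pump, so only the order of steps is missing. This stands in part: a taper completed before the visit satisfies both texts. But the order is exactly what decides what the final-visit records measure, and the SAP does not recover it.

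It is also fair that the outcomes affected are descriptive. The synopsis plans no formal testing, Protocol 8.0 says there is no efficacy endpoint, and the granuloma rates are untouched. No document shows that assessments were in fact made in different treatment states.

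Three stronger readings are tempting, and the documents do not support them:
- **Expanded access as a third treatment state.** It comes after the 12-month period, so it cannot change what is measured at the final visit. It is a disposition statement not reconciled with 9.5.
- **Up to 250 of 350 subjects affected.** 350 − 100 = 250 treats the 12-month target as attrition. Protocol 14.3 makes it a reporting threshold and allows subjects still on treatment at that point. Subjects lost to follow-up or withdrawing consent may also have no final visit at all.
- **Adverse-event counts turning on the drug-handling text.** That effect comes mainly from a separate conflict over when AE collection stops. Protocol 13.1 says it "ends after discontinuation of study medication", 5.1 runs it through the final visit, and 13.2.1 runs it to a follow-up telephone call. Reconciling drug handling would not settle that.

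**Conclusion.** The point holds for early discontinuers. The protocol gives them conflicting end-of-treatment handling and leaves the order of taper, removal and assessment unstated. The SAP then summarizes their records with those of Day 365 completers. Final-visit COWS, VASPI, BPI and PGIC can therefore mix drug states, with COWS the most affected.

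The size cannot be fixed from the documents; the margin of about 50 in 350 is the only indication of scale for departures before 6 months. The conclusion rests on two assumptions: that early-termination assessments are filed as the final visit, as 9.5 implies, and that sites may differ in whether they assessed before or after a taper. A reader might infer that all final-visit data are compromised. The order of sentences in 9.5 and the scope of 10.0 and 3.8 do not support that. The issue affects the interpretation of descriptive summaries, and is worth correcting because the correction is cheap.

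**What to change.** **Protocol.** Reconcile 9.5, footnote l (and its copy under SAP Table 1), 10.0, 3.8, 11.0 and the expanded-access sentence in the synopsis. Which clinical sequence is right is not for this review to say. SAP sections 2 and 8.4 report that all subjects have completed and the database is locked, so this cannot change conduct. The CSR should disclose the conflict and, as far as it is known, what was done.

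**SAP.** SAP 8.4 leaves the remaining analyses to be run on the locked data, so the following is still possible:
- From visit dates and the dose records already collected (SAP 9.3; Listings 16.2.14.1 to 16.2.14.4), classify each final-visit record as on drug, during taper or off drug. Where dates do not permit this, report the record as unclassified.
- Summarize Day 365 visits separately from early-termination visits for VASPI, BPI, PGIC and COWS.
- Show taper and off-drug COWS records in their own row. Excluding them would remove the records most likely to show withdrawal.

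**Cost.** A little more programming, smaller numbers in the Day 365 row, and some records that may stay unclassified because no further data cleaning is planned.
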